Most chronic neck pain is non-specific with no identifiable pathoanatomical cause (Beltran-Alacreu et al., 2018). Many therapies have been used to treat patients with chronic non-specific neck pain but exercise therapy is considered as the integral component of interventions (Blanpied et al., 2017). It has also been proved that exercise can reduce the symptoms of depression, anxiety and pain in patients with neck pain (Nazari et al., 2018). However, due to the lack of time, money and rehabilitation resources, many people cannot receive high quality conventional rehabilitation. Since the start of COVID-19 pandemic in 2020, it became more difficult to deliver the conventional form of exercise therapy to those patients with chronic neck pain by the physiotherapists. In response to this crisis, telerehabilitation, as a new service mode of delivering rehabilitation, has become popular for physiotherapists to treat various musculoskeletal, neurological and cardiopulmonary disorders (Havran and Bidelsbach, 2021). Telerehabilitation not only alleviates the time cost and economic cost of patients, but also reduces the pressure on the medical system (De Biase et al., 2020). In addition, online rehabilitation can maximize the use of high-quality rehabilitation resources, and neck pain patients in remote areas can also receive the cutting-edge and effective interventions at home. Recent review on systematic reviews of telerehabilitation in physiotherapy provides preliminary evidence that “telerehabilitation in physical therapy could be comparable with in-person rehabilitation or better than no rehabilitation for conditions such as osteoarthritis, low-back pain, hip and knee replacement, and multiple sclerosis and also in the context of cardiac and pulmonary rehabilitation” (Seron et al., 2021). However, the efficacy of telerehabilitation for patients with chronic non-specific neck pain is still unknown. A Cochrane review protocol on telerehabilitation for neck pain has been published but the review results are not available yet (Fandim et al., 2021).

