## **10. Interventions:**

Participants in both groups completed the same exercise program three times a week for six weeks with either face-to-face or online mode of delivery by physiotherapists.

At baseline, the suitable elastic bands (Thera-band®) for performing the exercises were selected by testing the 15 repetitions maximum (15RM) of the Modified Brügger's Exercise (MBE) and the Modified Proprioceptive Neuromuscular Facilitation Diagonal Flexion Exercise (MPNFDDE) for the participants of both the experimental group and control group. The details of the MBE and MPNFDDE were described in supplementary file 1.

Participants randomized to the control group performed the following exercises three times a week for six weeks in a group of 3-5 participants in the laboratory of the Sport Medicine and Rehabilitation School of the Beijing Sport University:

- A. Warm-up exercises
- B. Cranio-cervical flexion exercises
- C. Strength-endurance exercises
- D. Scapular stabilization exercises
- E. Stretching exercises

[figure not shown]
The details of the exercises were described in supplementary file 2.

Participants allocated to the experimental group performed the same set of exercise three times a week for six weeks in their home, with the following arrangements:

The participants had weekly online exercise meetings with the physiotherapist in a group of 3-5 participants using the TENCENT Meeting. Then the participants performed the remaining two sessions of exercises themselves weekly. If they had encountered any problems, they could consult the physiotherapist during the online session or texting to the physiotherapist using the WeChat app. All the participants of the experimental group received a package of exercise pamphlet and a video disc containing 17-minute exercise demonstrations by the physiotherapist.

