### **13. Statistical Analysis Plan:**

Continuous data were expressed as means and standard deviations. Categorical data were shown as frequencies or percentages. All statistical analyses were conducted using the IBM SPSS Statistics for Windows, Version 24.0 (Armonk, NY: IBM Corp). The normality of continuous data was checked with the Shapiro-Wilk test. The change scores of the primary and secondary outcome variables from baseline to end of intervention between the two groups were compared using independent sample t test. Within-group comparisons were done using paired sample t test. The level of significance of all statistical tests was set with two-tailed at 0.05. Per-protocol analysis was used. The sample size for the study was calculated to be 32 using the G\*Power 3.1.9.2 (Universitat Kiel, Germany), with an estimated effect size of group difference of 0.9 in primary outcomes and a level of significance of 0.05, statistical power of 80% with two-tailed independent sample t test. The estimated effect size was based on previous studies of home exercise on patients with neck pain (Zronek et al., 2016). With an anticipated dropout rate of 15%, a total of 39 participants was required.

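### The 0.9 SD group difference is not justified for a comparison of delivery modes, the stated 80% power is not reached even at 0.9, and p > 0.05 could not support comparable efficacy

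*Combined protocol and SAP*

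**What the plan says.** Section 13 (Statistical Analysis Plan) sizes the trial "with an estimated effect size of group difference of 0.9 in primary outcomes", at a significance level of 0.05 and "statistical power of 80% with two-tailed independent sample t test". On that basis, "The sample size for the study was calculated to be 32", raised to 39 for an anticipated 15% dropout. On where 0.9 comes from it says: "The estimated effect size was based on previous studies of home exercise on patients with neck pain". It does not give the comparator, outcome or SD in those studies.

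The same section fixes sidedness for every test: "The level of significance of all statistical tests was set with two-tailed at 0.05". Change scores are compared between arms by an independent-sample t test, within-group changes are examined by paired t tests, and the analysis is per protocol. It mentions neither a confidence interval for the between-arm difference nor a non-inferiority or equivalence margin.

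Section 10 (Interventions) describes the contrast: "Participants in both groups completed the same exercise program three times a week for six weeks". Controls attend small laboratory groups for their sessions. The online arm exercises at home, with one online group meeting and two unaccompanied sessions a week.

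Section 6 (Background and Significance) quotes an overview finding that "telerehabilitation in physical therapy could be comparable with in-person rehabilitation". It presents this as preliminary, for other conditions, and then says that efficacy in chronic non-specific neck pain is not known.

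**The concern.** A power statement is only as good as the difference it assumes. A difference of 0.9 SD is large, and the plan asserts it for two arms that share their exercise content. The plan gives no reason to expect a gap of that size from delivery and supervision alone. Smaller differences may still matter to patients, and the trial has little chance of detecting them.

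Interpretation is also at stake. Section 7 sets out to compare the efficacy of online and conventional exercise. The planned tests can easily produce significant improvement within each arm and p > 0.05 between arms. That pattern invites the conclusion that online delivery is as good, and the plan neither supplies an interval to show how much remains uncertain nor warns against that reading.

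**Working it through.** **Inputs from section 13.** Effect size 0.9, read as Cohen's d in SD units of the change score being tested; α = 0.05 two-tailed; power 80%; N = 32; dropout 15%; 39 enrolled.

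**Assumptions.** 1:1 allocation (the ratio is not stated). Completers: 39 × 0.85 = 33.15, taken as 33 and split 17/16.

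**Formula.** With df = n₁ + n₂ − 2 and noncentrality δ = d × √[n₁n₂/(n₁ + n₂)], power is the probability that a noncentral t(df, δ) variable exceeds the critical value t* in absolute size.

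**Step 1: the plan's own figure.**
- 16 per arm, two-tailed: δ = 0.9 × √8 = 2.546, df = 30, t* = 2.042. Power = 69.3%.
- 20 per arm, two-tailed: power = 79.2%.
- 21 per arm, two-tailed: δ = 0.9 × √10.5 = 2.916, df = 40, t* = 2.021. Power = 81.2%. The required total is therefore 42.
- 16 per arm, one-tailed 0.05: t* = 1.697. Power = 80.0%.

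So 32 is not reproduced with the stated two-tailed inputs, but is reproduced exactly with a one-tailed test. The normal approximation gives 20 per arm (40 in total), which is also not 32.

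The dropout step is sound: 32/0.85 = 37.6, so 38, within one of the stated 39. Starting from 42 it would be 42/0.85 = 49.4, so 50.

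**Step 2: what the planned size delivers.** For 17/16, √(272/33) = 2.871, so δ = 0.9 × 2.871 = 2.584; df = 31, t* = 2.040; power = 70.7%. The values 0.5 and 0.3 SD below are illustrative, because the documents give no alternative effect size.

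| Analysed | Power at 0.9 SD | at 0.5 SD | at 0.3 SD | Detectable with 80% power | 95% CI half-width |
|---|---|---|---|---|---|
| 32 (16/16) | 69% | 28% | 13% | 1.02 SD | 0.72 SD |
| 33 (17/16) | 71% | 29% | 13% | 1.01 SD | 0.71 SD |
| 39 (19/20) | 78% | 33% | 15% | 0.92 SD | 0.65 SD |

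Half-width = t* × √(1/n₁ + 1/n₂), in observed SD units. For 17/16 this is 2.040 × 0.348 = 0.71.

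**Step 3: what p > 0.05 would mean with 33 completers.**
- Observed difference zero: the interval runs from −0.71 to +0.71 SD.
- Observed difference just short of significance (0.71 SD): it runs from about 0 to 1.42 SD.
- The interval excludes 0.9 SD in both directions only if the observed difference is below 0.90 − 0.71 = 0.19 SD.

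**Step 4: would correcting 32 to 42 settle it?** No. With 42 analysed the half-width is 2.021 × √(2/21) = 0.62 SD. For 80% power at 0.5 SD, 128 would have to be analysed (151 enrolled after 15% dropout).

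**The case against.** Several stronger readings are tempting, and the documents do not support them.

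- **That the background expects no difference, so p > 0.05 is the likeliest result.** Section 6 calls the comparability evidence preliminary, draws it from other conditions, and says the neck-pain effect is unknown. That is uncertainty, not an expectation of zero.
- **That 0.9 belongs to a different contrast.** The comparator in the source studies is not given. If they compared home with supervised exercise, they could be close to this trial, since the online arm is home-based with two of three weekly sessions done alone. The documents show that the relevance of 0.9 is unargued, not that it is wrong.
- **That a null result would be uninformative.** An observed difference of zero would exclude differences beyond about 0.7 SD, including the design value of 0.9.
- **That the trial intends to claim equivalence.** The documents state no such aim or margin, and section 13 specifies an ordinary two-tailed test of difference. The risk is one of later interpretation.

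It may also be said that a sample-size section need not explain what a null result cannot mean. As a general rule that is fair. Here the shortfall in power, the missing interval and the paired within-group tests together make the misreading easy enough to justify a sentence. None of these objections touches the arithmetic.

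**Conclusion.** The point stands in three parts.

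1. The 0.9 SD is not justified for a contrast of delivery and supervision with shared exercise content.
2. The stated 80% power is not reached even if 0.9 is right. It is about 70% with 32 or 33 analysed and 78% if all 39 are analysed. This rests on 1:1 allocation and on taking the two-tailed specification at its word.
3. With about 33 completers, p > 0.05 would at best exclude very large differences. It could not support comparable efficacy, because differences of 0.3 to 0.5 SD would be detected only 13% to 29% of the time and the interval is about ±0.71 SD.

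The third part does not depend on the exact completer count: with all 39 analysed the interval is still ±0.65 SD. That 32 arose from a one-tailed setting is an inference from the exact match; the documents do not say so.

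**What to change.** Revise section 13, without enrolling more participants:

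- Restate the power as about 70% at 0.9 SD with the planned numbers, or give the difference detectable with 80% power as about 1.0 SD.
- Make the 95% confidence interval of the between-arm difference in change the main result for each primary outcome (average VAS, maximum VAS and NDI).
- State that neither p > 0.05 between arms nor significant within-group changes will be reported as comparable efficacy.

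Merely relabelling 0.9 as assumed would change nothing, since the plan already calls it an estimate. Adding an equivalence margin would be of little use at this size. In simulation with a true difference of zero and 33 completers, the 95% interval lies inside ±0.5 SD in under 0.1% of trials and inside ±0.7 SD in about 8%.

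The cost is a few sentences of SAP text, a lower stated power and a more modest conclusion.

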### **14. Informed Consent Process:**

Before participating in the study, physiotherapists will explain this study to all participants to ensure they are clear about this study. Participants can drop out at any time during this study. Then they will complete the informed consent form. All the participants are recruited from Beijing Sport University, China, and they are all native Chinese speakers, so the informed consent form is in Chinese (simplified). All participants should meet the inclusion criteria, and anyone meets the exclusion criteria will be excluded.

#### **Privacy and confidentiality:**

Subject's names will be kept on a password protected database, and they will be linked only with a study identification number for this research. There are no patient identifiers. All data will be entered into a computer that is password protected. Data will be stored in a locked office of the investigators and usually maintained for a minimum of three years after the completion of the study.

## **15. Risk/Benefit:**

### **Risk to participants:**

This is a relatively safe study which has rare risk. Since it is a training for neck muscles, it has possibility of muscle strain and worse neck condition. It has little risk of heart attack and other life-threatening conditions.

### **Benefits to Participants**

This study provides a good exercise plan for the participants which improves their neck functions and decreases their neck pain.

## **16. Study Timeline:**

Stage 1, screening, enrollment, ----2 weeks

Stage 2, treatment phase, ----6 weeks

Stage 3, data collection and data analysis, ----4 weeks

Stage 4, presentation and publication, ----1 year

## **17. Data Safety Monitoring:**

All data about participants that is collected during the course of the research will be kept strictly confidential. The data collected will be de-identified before being analysed, and identified data including medical history will be confidential and stored separately. However, confidentiality of participants' data is subject to legal limitations (e.g. subpoena, freedom of information claim, or mandatory reporting in some professions). All data will be kept in locked filing cabinets as well as password protected electronic files. Data will be securely stored for at least three years and may be kept indefinitely.

## **18. Conflict of Interest:**

No potential conflict of interest.

## **19. Publication and Presentation Plans:**

*List any meetings or conferences where you will be presenting the data and the results of your*

*study.*

